1.1 Data Management and Data Quality

The first randomization involves allocation to CPS vs. SMS using a 1:1 allocation ratio. This step will use stratified randomization in permuted blocks to achieve balance in distribution of behaviorally and perinatally infected youth. The REC data team will program the randomizer in Qualtrics and will not participate either in the intervention delivery or in the adherence reinforcement steps. The protocol team will monitor race, ethnicity, and gender to ensure balanced distribution at the first stage. After 6 months, stratified randomization will occur with permuted blocks within each trajectory. Since second stage randomization is dependent on first stage response status, we will only maintain the balance within each first stage treatment outcome when randomizing at the second stage.

Following the Analytic Core's (AC) standard quality assurance, including checking for outliers and abnormal values using graphical methods, we will verify that the distributions of measures meet the assumptions of the statistical tests to be used, applying a formal test such as the Shapiro-Wilk's test [60]. Transformations will be used when distributional assumptions are not fulfilled. Tests will be conducted to identify potential relationships among baseline demographic and clinical variables and our dependent variables and to see whether they are balanced between groups. If a baseline variable is not balanced between groups and is correlated with the dependent variable ($r > .30$), we will include this variable as a covariate in subsequent analyses. Since we will test more than one primary hypothesis with one primary outcome variable (VL suppression), the Hochberg step-up multiplicity adjustment will be used with a two-tailed family wise alpha-level of .05 [61]. All other tests described below will each have a two-tailed alpha-level of 0.05. Outcome analyses will be based on the principle of intention-to-treat [62].

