5.0 Procedures Involved*

Enrollment Procedures. Enrollment in this study may occur at any time during the recruitment period. Potential participants recruited utilizing the OneFlorida Data Trust will receive a “text-in” number, in which interested persons will be able to text-in to receive instructions for screening and enrollment. Potential participants through the OneFlorida Data Trust who do not “opt-out” of being contacted could also be directly contacted by the study team to be informed of the study and screening/enrollment options for preliminary eligibility.

Screening and enrollment may occur on the same day, as long as the appropriate VL and ART regimen data are appropriately obtained. If a participant is determined to be eligible for the study, a unique Qualtrics link will be sent to the participant for submitting proof of HIV VL ≥ 200 copies/mL and ART regimen. After final eligibility is determined, study staff sends the potential participant the SMART enrollment link, which contains the study

PROTOCOL TITLE: ATN 144 SMART

consent/assent form, HIPAA Authorization form, and the baseline web-based survey. These are programmed in Qualtrics by the REC. The baseline survey can be completed at the participant's convenience (ideally within 14 days before and 28 days after their scheduled assessment date). Upon completion of all portions of the enrollment link, participants are considered enrolled in SMART. Study staff will then randomize and stratify the participants into their respective intervention arms (CPS or SMS) for the first period of the study. Stratification is based on method of contraction: Perinatal vs Behavioral (and other).

Participants randomized to the CPS intervention group will speak with the AF to determine the start day and call time for intervention phone calls. This phone call should be completed within 30 days from entry. Participants randomized to the SMS intervention will speak with the Project Coordinator (PC) to identify the start day, timing, and content of the text messages they will begin receiving daily.

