1.2.4 Sample Size and Power

Sample Size and Power. Statistical power analyses examined the sample size requirements to detect greater than chance group differences on primary outcome (PH1 and Ph2). We have used Susan's formula with a total sample size of 120.

<http://people.seas.harvard.edu/~samurphy/papers/APPProof.pdf>

| Power Table | | | |
|--------------------|------------|------------|-----------------------------|
| ES | p | N | N(10% attrition adjustment) |
| 0.55 | 0.4 | 86 | 96 |
| | 0.5 | 104 | 116 |
| | 0.6 | 130 | 144 |
| | 0.7 | 174 | 192 |
| 0.6 | 0.4 | 74 | 80 |
| | 0.5 | 88 | 98 |
| | 0.6 | 110 | 120 |
| | 0.7 | 146 | 160 |

Alternatively, for the two groups comparison this corresponds to n=60/group. This sample size is sufficient to provide 80% power (or more) for a standardized Effect Size (ES) of 0.55 or more, using a t-distribution for a two tailed test with $\alpha=0.05$, with 10% attrition assuming equal responder rate (p) in both arms.

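### The imbalance-and-correlation rule makes covariate choice data-driven and leaves baseline log10 viral load and the true randomisation stratifier unspecified in the primary analyses.

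*SAP*

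**What the plan says.** SAP 1.1 (same text in Protocol 16.0) first tests baseline variables for balance and for association with the outcome. It then applies two conditions jointly: "If a baseline variable is not balanced between groups and is correlated with the dependent variable". The second has a threshold and a consequence: "correlated with the dependent variable ($r > .30$), we will include this variable as a covariate in subsequent analyses". No cut-off defines imbalance, and nothing says which post-baseline value the correlation uses.

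SAP 1.2.1 describes two kinds of primary analysis:

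- A first-stage comparison of cell phone support (CPS) with text messaging (SMS), by chi-square and two-sample t-test, with no covariate named.
- Linear mixed models for the two primary hypotheses. These always contain clinical site, age and gender, take week 0 as one of the repeated outcomes, and reject on the group-by-time interaction.

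Site, age and gender are described there as the stratification variables. Protocol 5.0 says otherwise: "Stratification is based on method of contraction: Perinatal vs Behavioral (and other"). SAP 1.1 agrees with Protocol 5.0 that the blocks are stratified on behavioural versus perinatal infection.

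**The concern.** In a randomised comparison, what adjustment buys depends on how well the covariate predicts the outcome. Chance imbalance is a poor condition to add, because randomisation makes it rare. Requiring both conditions means a strong predictor is usually discarded, and the covariate set is fixed only after outcome data have been seen.

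Two variables are affected. Baseline log10 viral load is an obvious candidate predictor and is named as a covariate nowhere. Mode of infection was used to stratify, so the analysis would normally condition on it. Under the plan it can enter only if it is imbalanced, which stratified permuted blocks are meant to prevent.

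The stake is efficiency and prespecification in a trial of 120 whose stated power sits close to 80%.

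**Working it through.** **Inputs from the documents.** Allocation is 1:1 (SAP 1.1). SAP 1.2.4 gives the size ("for the two groups comparison this corresponds to n=60/group"), the test ("using a t-distribution for a two tailed test with $\alpha=0.05$, with 10% attrition") and the claim: "This sample size is sufficient to provide 80% power (or more) for a standardized Effect Size (ES) of 0.55 or more". After 10% attrition, 60 × 0.9 = 54 per group.

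**Assumptions, not in the documents.** The correlation of a baseline covariate with the outcome is taken as 0.2 to 0.5. The imbalance cut-off is taken as p<.05, with p<.20 as a loose alternative. The correlation condition is read as |r| > .30 unless stated. The outcome is continuous.

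**1. The plan's own figure.** n per group = 2(1.96 + 0.84)² / 0.55² = 51.9, so 52 per group or 104 in total. 104 / 0.9 = 115.6, so 116. This matches the table row for effect size 0.55 and p = 0.5 (104 and 116) and fits within 120. Power at 54 per group is 80.8% by the t-distribution. The claim reproduces, with no covariate gain assumed.

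**2. How often the rule lets a covariate in.** Under randomisation, a balance test at p<.05 is passed by chance in about 5% of trials, and the correlation condition can only lower that. Simulation at 54 per arm gives the entry rates in the table. At p<.20, entry is roughly 16-20% for correlations of 0.4-0.5.

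**3. Power of the first-stage comparison.** Adjustment multiplies the residual variance by 1 − r², so the effective effect size is d / √(1 − r²). With d = 0.5 and 54 per arm, unadjusted power is 73%.

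| r | 1 − r² | covariate enters (p<.05) | power under rule | power if always adjusted |
|---|---|---|---|---|
| 0.2 | 0.96 | under 1% | about 73% | about 74% |
| 0.3 | 0.91 | about 2% | about 73% | about 77% |
| 0.4 | 0.84 | about 4% | 73-74% | about 80% |
| 0.5 | 0.75 | 4-5% | about 74% | about 84% |

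A looser cut-off recovers little: at r = 0.5 and p<.20, power under the rule is about 76-77%. At the SAP's own effect size of 0.55, always adjusting raises 80.8% to 82.4%, 84.3%, 87.1% and 90.5% for the same four correlations.

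**4. Type I error.** With no true effect and r of 0.4-0.5, the rule rejects in about 4.1-4.6% of trials. It is slightly conservative, not inflated.

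**5. The mixed-model test.** With five equally spaced visits (weeks 0, 12, 24, 36, 48), complete data and within-subject correlation ρ, the variance of the difference in slopes is 2(1 − ρ)σ² / (n·Sxx), with time coded 0 to 4 so that Sxx = 10. For ρ = .30 and n = 54 this is 2 × 0.70 / 540 = 0.00259 in units of σ². Between-participant intercept variance does not appear in it. A baseline main effect explaining up to 64% of that intercept variance leaves the result unchanged (ratio 1.000) for ρ = .30, .40 and .50, the values in Protocol 16.0. The same holds with an uncorrelated random slope added.

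**6. Stratification, side by side.** Protocol 5.0 and SAP 1.1 stratify on mode of infection. SAP 1.2.1 and the analysis text of Protocol 16.0 name site, age and gender instead. Neither model list contains mode of infection.

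**The case against.** The strongest reply is that the rule matters less than it looks, and much of this stands.

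- A reader might infer that covariates enter only through the rule. They do not: site, age and gender are always in the mixed models.
- A reader might infer that baseline viral load is almost never used. That is too broad. Week-0 suppression is a response in the first-hypothesis model, and Protocol 16.0 also compares the drop in log10 viral load. The reply has limits: participants who enter on a viral load of at least 200 copies/mL are nearly all unsuppressed at week 0, so the binary value carries little of the continuous information; and the second-hypothesis model uses self-reported adherence as its response, so baseline viral load is absent there.
- A reader might carry the 7-10 point loss at correlations of 0.4-0.5 over to the decision test. Step 5 shows that it does not transfer in complete data. Missing visits or covariate-by-time terms could change that.
- The documents give no correlation of baseline viral load with either outcome. At 0.2-0.3 the gain is only about 1-3 points.
- Read literally, r > .30 excludes negative correlations, the expected sign between baseline viral load and suppression; the rule would then never adjust (73% against 84% at −0.5). Shorthand for strength of correlation is the likelier meaning, and reading it as |r| still leaves power at about 74%.
- Data-dependent selection might suggest false positives. Step 4 shows none.

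What the reply does not answer is that SAP 1.2.1 calls the first-stage comparison the primary analysis yet names no covariate for it, and that the true stratifier is missing from the models.

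**Conclusion.** The point holds as a loss of efficiency and prespecification, not as an invalid test. Beyond site, age and gender, a prognostic baseline variable enters in about 5% of trials or fewer if imbalance means p<.05, and in about 20% at most if it means p<.20. For the first-stage comparison at 54 per arm and 0.5 SD, the cost is about 1 point of power at a correlation of 0.2, 3 at 0.3, 6-7 at 0.4 and 10 at 0.5. These sizes rest on assumed correlations and on a continuous outcome; for a binary outcome they are only a guide. No gain is claimed for the mixed-model interaction test. The omission of mode of infection and the misnamed stratification variables rest on the text alone and need no assumption.

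**What to change.** - Delete the imbalance-and-correlation rule from SAP 1.1 and Protocol 16.0.
- Prespecify mode of infection (perinatal versus behavioural and other) in every primary model, and stop describing site, age and gender as stratification variables. They may remain as covariates.
- Replace the first-stage chi-square and t-test with a regression (logistic or ANCOVA) adjusted for mode of infection, baseline log10 viral load and the baseline value of the outcome.
- In the mixed models, do not add the week-0 outcome as a covariate while it is also a response row. In particular, week-0 adherence should not be both in the second-hypothesis model. Baseline log10 viral load may be added where it is not the response.

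No new data are needed: baseline viral load, adherence and mode of infection are already collected. The cost is revised SAP text, a changed first-stage method and a few degrees of freedom. Participants without a baseline viral load need handling under the multiple imputation planned in SAP 1.2.5. The change should be fixed before outcomes are examined by arm.

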1.2 Quantitative Analysis Plan

Original Primary Hypotheses: 1. Youth randomized to CPS will have significantly greater VL suppression (primary outcome) and self-reported medication adherence (secondary outcome) at 24 weeks than those in SMS group. 2. Non-responders randomized to CPS with incentives will have significantly greater VL suppression (primary outcome) and self-reported adherence (secondary outcome) than those randomized to SMS with incentives.

Original Secondary Aims: a) Conduct an exploratory evaluation of tapering the intensity of CPS and SMS (among responders) vs termination after completion of the 24 week intervention to determine if this improves the durability of intervention effects; b) Explore the relative efficacy of the individual intervention sequences embedded within the SMART design for responders and non-responders; and c) Describe moderators of the treatment effect, including demographics, mode of infection, substance use, and mental health. [NOT COMPLETED DUE LOW RENTENTION]

Updated Primary Outcome: Originally, we plan to treat VL suppression as our primary outcome for both co-primary hypothesis. Primary end-point for H1 was at 24 weeks when the proximal outcome was used to determine responder status, while for H2 the Distal outcome was at end of 12 months (or 72 weeks). Due to the difficulty in collecting viral load we proposed to change the primary outcome to a combination of VL suppression and self-reported adherence (SRA). Primary end-points for both co-primary hypothesis is now at 48 week.

Rationale of new definition of Primary Outcome: Since the VLS data may not be available for a significant number of subjects, we plan to use SRA as an additional primary outcome. The usefulness and appropriateness of the usage of these two depends upon the concordance of two measures. To determine that for those subjects we have both VLS and SRA data available, we will first construct a 2×2 contingency table and conduct a chi-square test of association. If they agree on 80% or more cases we will proceed to define (and analyze) the primary outcome as following:

- 1) For any data collection point and randomization event, if VLS data is available it will be used as primary outcome. When VLS data is not available, SRA will be used as primary outcome. This composite definition will be used as primary outcome and will have sufficient power based on hypothesized effect size.
- 2) In case it fails to agree at least 80% cases, we will analyze VLS and SRA as two separate primary outcomes. Two measures cannot be combined, as they do not match sufficiently. In this situation, it is likely that VLS as primary outcome will not have sufficient sample size to produce an appropriately powered analysis, albeit, SRA may still produce a powered analysis provided SRA is available for all subjects. Note though no conclusion about VLS can be drawn from the outcome of SRA analysis.

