	
medication and participants will text back a confirmatory response. The CPS intervention will occur on weekdays, excluding holidays. The SMS intervention will occur every day. The tapered intervention will occur on two weekdays per week, excluding holidays. Incentives will be added to the intervention for those participants who do not meet viral suppression requirements at 3 months.
 
Sub-study: Project DABS does not implement any interventions.

Study Population
	
The study population will consist of HIV-positive youth (15-24 years old, inclusive) who have: a VL ≥ 200 copies/mL within 12 months prior or self-reported adherence (SRA) $\leq 80\%$ in the past 4 weeks after being on a prescribed ART medication regimen for three months prior to eligibility VL; a cell phone and service plan; and the ability to understand written and spoken English.
 
Sub-study:
 
Youth (15-24 years of age) living with HIV (YLH) who are willing to provide DBS specimens for HIV VL measurement and have the ability to understand written and spoken English.

Sample Size
	
We will enroll 120 HIV-positive youth living with HIV aged 15-24.
 
Sub-study: 50

Study Duration for individual participants
	
The total duration of the study for participants is approximately 12 months for both groups.
 
 • Baseline Assessment • Follow Up Assessment (post baseline) 
 ○ 3-Month Follow Up ○ 6-Month Follow Up ○ 9-Month Follow Up ○ 12-Month Follow Up 
Sub-study: approximately 1 month

Study Specific Abbreviations/ Definitions
	
Adherence Facilitator (AF) Adolescents Medicine Trials Network (ATN) Cell Phone Support (CPS) Cell Phone Support + Incentives (CPS-I) Cell Phone Support Tapered (CPS-T) Sequential Multiple Assignment Randomized Trial (SMART) Text Messaging (SMS) Text Messaging + Incentives (SMS-I) Text Messaging Tapered (SMS-T) Youth living with HIV (YLH) ART – antiretroviral therapy CASI – computer assisted self-interviewing

PROTOCOL TITLE: ATN 144 SMART

	
DBS – dried blood spot HIV – human immunodeficiency virus PI – principal investigator VL – viral load

--	--

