At each follow-up, participants will complete web-based surveys programmed in Qualtrics by the REC. A link to these computerized surveys will be sent to each participant by the REC and can be completed at the participant's convenience (ideally within 14 days before and 28 days after their scheduled assessment date). Participant VL data will need to be obtained before the study procedures for the respective assessment period is considered complete and the participant is compensated. Data files will be downloaded via Qualtrics by the Data Management Team of the REC. The REC will maintain a linkage of PID and subject name, and these will be stored in password protected files. These web-based surveys will take approximately 60-90 minutes to complete.

Randomization Process/Systems. Participants will be randomized at the end of their baseline assessment into one of two intervention conditions: (1) CPS or (2) SMS. Both intervention conditions will receive 3 months of intervention (i.e., 3 months of CPS or SMS). Each participant's condition will be tracked in REDCap. At the 3-month follow-up, a second stratified randomization will occur in blocks with 8 possible intervention trajectories as follows:

- CPS responders (VL <200 copies/mL) will be randomized to either 9 months of standard care (SC) or 3 months of CPS-T followed by 6 months of SC;
- CPS non-responders (VL \geq 200 copies/mL) will be randomized to 3 months of CPS-I or SMS-I followed by 3 months of CPS-T or SMS-T, respectively, and then 3 months of SC for both groups thereafter;
- SMS responders (VL <200 copies/mL) will be randomized to either 9 months of SC or 3 months of SMS-T followed by 6 months of SC; and
- SMS non-responders (VL \geq 200 copies/mL) will be randomized to 3 months of CPS-I or SMS-I followed by 3 months of CPS-T or SMS-T, respectively, and then 3 months of SC for both groups thereafter.

Participants who are unable to provide a valid HIV VL result at the 3-month time point have approximately 30 days to obtain a HIV VL performed at Quest Diagnostics or have a physician release this information to PRIDE. Participants who are unable to provide this

PROTOCOL TITLE: ATN 144 SMART

information within the timeframe i.e. 30 days after their 3 month follow-up assessment will be treated as non-responders to the intervention and will be re-randomized to an incentive arm. The 30 day window follows the same timeframe as the 30 day window for calls to begin following baseline.

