Participants may submit VL test results from their standard care providers (at both SRV and non-SRV clinics) as long as they were measured using a level of detection of <200 copies/mL or below and the VL collection dates are within 6 months prior to screening or the baseline assessment, and within 2 weeks prior to or 4 weeks after all other study follow-up assessments. VL measurements using a level of detection ≥ 200 copies/mL will not be accepted. If participants have a standard care provider, but no VL test results

PROTOCOL TITLE: ATN 144 SMART

within the required window period, they may request a new VL test from their usual provider and invoice the REC.

If participants decide to obtain a copy of their standard care VL test results, they will be given two choices on how to submit their VL test results. The REC will inform the participant that they may take a picture of their newly obtained standard care VL test result using their personal cell phone and submit the picture through a secure Qualtrics online submission form. Participants may also request their providers directly send their newly obtained lab results to the REC. This option may require youth to provide a release of information (ROI) if one is not already in place.

If standard of care results are not available, participants who have access to a clinical SRV, but have not completed a VL test within the required window period may request a new VL test for research purposes. The REC will refer participants to a clinical SRV; participants do not need to be an existing patient or establish care at this clinic in order to complete this study component. This new test will be invoiced to the REC and not billed to the patient's insurance. Clinical care VL measurements can be used as long as they were measured using a level of detection of <200 copies/mL or below. VL measurements using a level of detection ≥ 200 mL will not be accepted. Participants should complete this VL test within 1 month of screening before the baseline assessment, and within 2 weeks of each follow-up assessment. The REC will contact providers to submit VL measurements via fax or Qualtrics.

Participants who cannot or do not wish to visit a medical provider may be referred to local Quest Diagnostics labs for VL testing. The REC will order and pay for these labs, and receive VL data directly via online.

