Submitting the viral load result within two weeks of the date link is sent out (bonus)	\$ 10.00
Completing the survey within one week of the date is sent out (bonus)	\$ 10.00
9-Month Assessment Compensation	\$ 110.00
Submission of the viral load result	\$ 45.00
Completion of the survey	\$ 45.00
Submitting the viral load result within two weeks of the date link is sent out (bonus)	\$ 10.00
Completing the survey within one week of the date is sent out (bonus)	\$ 10.00
12-Month Assessment Compensation	\$ 120.00
Submission of the viral load result	\$ 50.00
Completion of the survey	\$ 50.00
Submitting the viral load result within two weeks of the date link is sent out (bonus)	\$ 10.00
Completing the survey within one week of the date is sent out (bonus)	\$ 10.00
Total Compensation (upon completion of all 5 assessments)	\$ 500.00

Measures. Baseline data collections should be completed all within the same day, and ideally no later than 7 days after the beginning of the baseline. Follow-up data collections should be collected up to 14 days prior to target date and up to 28 days after the target date. Due to COVID-19 pandemic, 12-month assessment window will be extended to 90 days. Those who are overdue for 12-month assessment will be allowed to complete the CASI and submit the VL after their window is closed. These participants will receive 90 days extension to complete the last component of the study. The REC Data Management Team will monitor reports of when participants are due for follow-up assessments. Self-report measures will be collected via a link to Qualtrics which can be accessed via smartphone, laptop, or PC. Site characteristics, including resources and supports available for non-adherent youth living with HIV, will be recorded into a Qualtrics survey and managed by the REC.

PROTOCOL TITLE: ATN 144 SMART

[figure not shown]
Web-based CASI Measures	Baseline	Follow-Up
Demographics		
Demographics/Socioeconomic Characteristics (ATN)	X	
Primary Outcomes		
HIV Positive Cascade: Medication Adherence Variables	X	X
Viral Load	X	X
Other Self-Reported Measures		
HIV Positive Cascade: Other Participant Characteristics	X	X
Self-Efficacy for Medication Adherence	X	X
Sexual Risk Behavior Questionnaire (harmonized + additional questions)	X	X
Additional Self-Management Measures		
Substance Use: ASSIST	X	X
PHQ-8 (Depression)	X	X
GAD7	X	X
PROMIS: Emotional Support, Informational Support, Instrumental Support, Companionship, Social Isolation	X	X

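### The 80% VLS–SRA agreement check in SAP 1.2 does not exclude baseline pairs, although entry already selects on the same two variables

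*SAP*

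**What the plan says.** SAP 1.2 sets a gate before the primary outcome is fixed. The comparison is made "for those subjects we have both VLS and SRA data available, we will first construct a" 2×2 table. "If they agree on 80% or more cases we will proceed to define (and analyze) the primary outcome as following": VLS where it exists, and "When VLS data is not available, SRA will be used as primary outcome". Below 80%, "we will analyze VLS and SRA as two separate primary outcomes", and the SAP expects VLS to be underpowered in that case.

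The SAP does not say which visits enter the table, whether a case is a person or a person-visit, what SRA cut defines adherence, or how close in time the two measures must be. The composite that follows the gate applies at every data collection point, and SAP 1.2.1 models week 0 with the later visits.

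Entry is defined on the same two variables. The Protocol's Study Summary and section 9.0 admit youth with VL of 200 or more, or with SRA of 80% or less "in the past 4 weeks after being on a prescribed ART medication regimen" for three months. Section 5.0 (enrollment procedures) asks for proof of VL of 200 or more, and section 13.0 drops people whose VL proves suppressed.

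At follow-up, section 5.0 accepts provider VL results "within 2 weeks prior to or 4 weeks after all other study follow-up assessments" and surveys "ideally within 14 days before and 28 days after their scheduled assessment date". It adds: "Due to COVID-19 pandemic, 12-month assessment window will be extended to 90 days".

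**The concern.** An agreement check is informative only if all four cells of the table are free to fill. At baseline they are not, because people who are both suppressed and adherent are the ones the entry rule keeps out. Baseline agreement is then partly a product of the eligibility criteria.

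The threshold chooses between two different primary analyses: one composite, or two separate outcomes with VLS probably underpowered. If baseline pairs are pooled with follow-up pairs, the choice can turn on how participants were recruited and not on whether self-report is an adequate proxy for VL.

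**Working it through.** **The plan's own figure.** No operating characteristics are given for the 80% gate, so there is nothing to reproduce for it. The nearest figure is the power in SAP 1.2.4. With 60 × 0.9 = 54 per group and effect size 0.55, power is Φ(0.55 × √(54/2) − 1.96) = Φ(0.90) = 0.815, which agrees with the stated 80% or more. It does not bear on the gate.

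**Step 1: what entry does to the table.** Let the shares be a (suppressed, adherent), b (suppressed, not adherent), c (unsuppressed, adherent) and d (unsuppressed, not adherent). Agreement before selection is a + d. All cell values below are assumed.

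- *Entry on either criterion* removes a, so agreement becomes d/(b + c + d).
  - With a = d = 0.40 and b = c = 0.10: 0.40/0.60 = 66.7%, against 80% before selection.
  - With a = d = 0.425 and b = c = 0.075: 0.425/0.575 = 73.9%, against 85%.
  - Under this rule selection can only lower agreement, because d/(1 − a) ≤ a + d reduces to a(1 − a − d) ≥ 0, which always holds.
- *Entry on proof of VL of 200 or more* removes a and b. One row remains, the chi-square test is undefined, and agreement is d/(c + d), the share of unsuppressed youth reporting low adherence.
  - With a = 0.50, b = 0.05, c = 0.15, d = 0.30: 0.30/0.45 = 66.7%, against 80%.
  - With b and c exchanged: 0.30/0.35 = 85.7%, against 80%. Under this rule the bias can go either way.

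The empty cell presumes that the table's adherent category lies above the 80% entry cut and that the entry values also serve as the baseline values. The SAP states neither, hence empty or nearly so.

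**Step 2: effect on the gate.** Assumptions: a case is a person-visit; pairs are independent; there are 120 baseline pairs; follow-up pairs m are 144, 240 or 336 (30%, 50% or 70% of 120 × 4 = 480). Let A_b and A_f be baseline and follow-up agreement. Pooled agreement is (120·A_b + m·A_f)/(120 + m), and it equals 80% at A_b = 0.80 − (A_f − 0.80)·m/120. Pass probabilities are exact binomial; pooled agreement is in brackets.

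Follow-up agreement 85%:

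| m | Fails if A_b is below | Pass, follow-up only | Pass, A_b = 73.9% | Pass, A_b = 66.7% |
|---|---|---|---|---|
| 144 | 74% | 0.942 | 0.480 (80.0%) | 0.087 (76.7%) |
| 240 | 70% | 0.986 | 0.762 (81.3%) | 0.327 (78.9%) |
| 336 | 66% | 0.994 | 0.885 (82.1%) | 0.559 (80.2%) |

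The 73.9% column is the like-for-like case: 85% agreement throughout, with baseline altered only by the either-or entry rule.

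Follow-up agreement 75%:

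| m | Passes if A_b is above | Pass, follow-up only | Pass, A_b = 95% |
|---|---|---|---|
| 144 | 86% | 0.072 | 0.964 (84.1%) |
| 240 | 90% | 0.041 | 0.820 (81.7%) |
| 336 | 94% | 0.017 | 0.576 (80.3%) |

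**Step 3: age of the baseline VL.** Protocol 5.0 allows a screening VL as baseline if the other components follow within 1 month, with exceptions by approval. The same section accepts provider results up to 6 months old. Section 9.0 allows 12 months for eligibility. The three are not reconciled.

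**Step 4: gaps at follow-up.** If survey and VL each float around the visit date, they can be 14 + 28 = 42 days apart. At month 12 the limit is 14 + 90 = 104 days, or 14 + 28 + 90 = 132 if the extension is added to the usual limit. If the VL window is read as relative to the survey, the usual maximum is 28 days. These are limits; the typical gap is not given.

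**The case against.** **The SAP is silent on baseline; it does not say baseline pairs will be used.** This is true. The sentence placing both endpoints at week 48 comes shortly before the table, so a week-48 or post-baseline table is a fair reading. That limits the point to an omission, but an omission in a rule that selects the primary outcome should still be closed.

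**A reader might infer that poor timing alone will probably fail the gate.** With independent, uniform dates over 42 days, (1 − 14/42)² = 44% of pairs are more than 14 days apart. Over 104 days at month 12, 75% exceed 14 days and 53% exceed 28. If agreement is 85% for well-timed and 70% for badly timed pairs, 0.85 − 0.15 × 0.444 = 78%. The documents do not support this:

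- Protocol 5.0 pays bonuses for a survey within one week and a VL within two weeks of the link, which should draw the dates together. The month-12 extension covers survey and VL alike.
- A gap of 15 days still lies inside a 4-week recall. Only (1 − 28/42)² = 11.1% exceed 28 days, and the same formula then gives 0.85 − 0.15 × 0.111 = 83%, a pass.
- The 4-week recall is stated only for eligibility, and the 85% and 70% rates appear nowhere in the documents.

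**A strict date limit has its own cost.** SRA would replace VL under the actual visit windows, so keeping only well-timed pairs could flatter SRA and would discard scarce data. This stands, and it argues for a sensitivity analysis in place of an exclusion.

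**The gate may not decide anything.** SAP 1.2.1 names SRA as primary without mentioning the gate and demotes VL suppression. This also stands: the gate selects the primary outcome only if SAP 1.2 prevails.

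**Conclusion.** The point holds for baseline pairs. They cannot show how well SRA stands in for VL, and nothing in SAP 1.2 keeps them out of a table that may choose the primary outcome. The structural finding needs only the entry criteria and an adherence cut consistent with them. Its size rests on the assumed agreement rates, pair counts and independence in the working, because the documents give none.

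The timing of follow-up pairs is a secondary matter of specification: wide gaps are permitted, but no figure for how common they are can be drawn from the documents. This should be corrected before the agreement table is run, though it is less basic than the conflict between SAP 1.2 and 1.2.1 over what the primary outcome is.

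**What to change.** In SAP 1.2:

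- Compute the gating agreement on post-baseline pairs only, and show the baseline table separately as descriptive.
- State whether a case is a person or a person-visit, and give the SRA cut and recall period used for the table.
- Report agreement by days between VL collection and survey completion, including a within-14-days subset, as a sensitivity analysis and not an exclusion. Protocol 5.0 already uses two weeks for clinic-ordered follow-up tests.
- Give a confidence interval for the agreement figure.

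Reconcile SAP 1.2.1 with SAP 1.2 on whether SRA is primary regardless of the gate. Reconcile the 1-, 6- and 12-month rules for the baseline VL, and the two statements of the entry criterion. SAP 1.2 carries a note about low retention, so if agreement has already been examined, label the restricted table post hoc.

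The cost is a few sentences of SAP text, fewer pairs and a wider interval around the agreement figure. No new data should be needed, since VL collection dates and survey completion times are required to apply the windows and pay the bonuses.
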